## Procedure and setting

Following the approach of community-based participatory research, we worked with a community agency, [blind for review], the largest organization serving dementia caregivers in New York City (NYC). Before designing the intervention, we conducted in-depth interviews with 30 caregivers and a survey with 168 caregivers to understand caregivers' needs, challenges, strengths and resources [Blind for review]. We also studied the utilization, effectiveness and limitations of existing services for these caregivers from a focus group with social work professionals [Blind for review]. Based on the empirical evidence, we concluded that a peer mentoring intervention may help reduce Chinese American caregiver reduce stress. We established a community advisory committee, including one social work professional, one administrator and three caregivers, and gathered their insights on the development of the intervention. We sent the first and second drafts of the intervention manual to committee members, collected their feedback from committee meetings, and revised the manual based on their feedback. After a pilot test, we presented the results in community events to dementia caregivers, professionals and administrators for their comments to improve the intervention for a larger-scale test.

We developed the intervention and conducted the pilot test in NYC, the metropolitan area with the largest Chinese American population in the United States. Based on 2017 census estimates, 893,697 Chinese live in NYC, and most Chinese older adults live in ethnic enclaves such as Chinatown (U.S. Census Bureau, 2017). In the past three decades, bilingual professionals in [blind for review] had provided various services, such as group training,

public lectures, mental health counseling, to support local Chinese older adults and their family caregivers. However, many Chinese caregivers in NYC have challenges accessing individually tailored support due to the shortage of bilingual and bicultural professionals.

#### Intervention

The PMP was a 3-month intervention that provides one-on-one mentoring support via phone calls to reduce the stress of Chinese dementia caregivers. Guided by the conceptual framework shown in Figure 1, the peer mentoring support covered the themes of cultural beliefs about dementia, culturally effective coping strategies, and culturally appropriate social support. The program recruited and trained Chinese American experienced caregivers to be volunteering mentors for dementia caregivers in the same ethnic community. Prior to mentoring caregivers, the mentors received training on knowledge about dementia, caregiving skills, social support, and problem-solving strategies. A social worker led the training workshop via lectures, discussions, and role-play practice, in which mentors could learn how to deliver knowledge and skills in a culturally competent way to their mentees.

Due to the COVID-19 pandemic, the mentor training workshop was delivered in five synchronous online sessions and each session lasted for 4 hours with two 10-minute breaks.

With technology support provided by the research assistants, mentors did not have any technology issues and appreciated the convenience of having the training via the internet.

Each mentor was paired with one to three caregivers based on their language preference and similar caregiving experiences (e.g., relationship with care recipient). During the 3-month intervention, each pair of mentor—mentee was expected to have one weekly phone call, which lasted for 30 to 60 minutes. After each call, the mentor was required to

document major issues and strategies covered in the call by filling the mentoring record form.

A social worker supervised mentor's work by reviewing mentoring records and facilitated biweekly meetings with mentors to address questions or issues related to the intervention.

## Sample

We recruited caregivers and mentors through referrals by [blind for review] and distributing flyers in community events as well as the agency's monthly letters to clients, senior centers, hospitals, geriatric clinics, and community agencies serving Chinese older adults in NYC. Trained research assistants conducted screening interviews with caregivers and mentors who expressed interest to the study. The eligibilities for being a participating caregiver were: (a) self-identify as Chinese; (b) 21 years old or older; (c) providing care to a family member with dementia for 10 hours or more a week; (d) interested in receiving supportive interventions; (e) having moderate to severe caregiver burden; and (f) able to access a telephone and communicate via phone call. The eligibility of being considered as a mentor were: (a) 50 years old or older; (b) self-identify as Chinese; (c) able to speak Mandarin or Cantonese Chinese; (d) having experience of providing care to a family member with dementia; (e) able to access a telephone and communicate via phone call; (f) able to attend mentor training via zoom; and (g) committed to volunteering with minimal financial compensation. Caregivers and volunteer mentors were excluded if they had cognitive impairment. We aimed to develop the intervention as a senior volunteer program, so mentors were limited to those aged 50 or older. We recruited 45 caregivers and 10 volunteers who expressed interests and participated in the screening interviews. Our final sample for this pilot study included 38 Chinese caregivers and 8 mentors who met the above criteria. The enrolled caregivers were randomly assigned to the intervention group (n=19) and the control group (n=19). The intervention group received 3-month mentoring support and the control group received a package of educational materials on knowledge of dementia, caregiving skills, self-care and community resources. A caregiver participant received a \$30 gift card after each assessment at baseline (T1), 3-month follow up (T2), 6-month follow up (T3). A volunteer mentor received a \$100 gift card after completing the training and another \$100 gift card after the 3-month mentoring service and assessments at T1 and T2.

#### Analysis

For the feasibility test, we calculated relevant percentages and means across the intervention study measurements. We also transcribed and coded the qualitative data from the open-ended questions to identify strengths and weakness of the intervention design and implementation. For the efficacy test, we conducted t-test to compare outcome variables across T1 to T3, and changes between time points (T2-T1, T3-T2, T3-T1) between the two groups. We also conducted difference in difference (DID) analysis using the *mixed* command in Stata. In multilevel (observations nested in caregivers) linear regression models, we first entered group, time and the interaction term of group and time and then entered covariates, such as sociodemographic, health, acculturation and caregiving variables, one by one due to the small sample size. None of the covariates changed the main findings, so we did not report those parameters in this paper. We missed three caregivers' data at T2 and T3. Two caregivers (one in the intervention group and the other in the control group) lost their care recipients during the intervention time and most measures (e.g., caregiving burden, caregiving competency) were not applicable to them. One caregiver in the control group

dropped off the study due to tight personal schedule. Given the purpose and sample size of this pilot study, we did not perform imputations or replications for missing data.

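### The efficacy test relies on unadjusted level and change t-tests with no lead contrast named; one T1-adjusted comparison at T2 would be more precise and give one answer.

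*Combined protocol and SAP*

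**What the plan says.** The Analysis section of the combined protocol and SAP describes a single efficacy test with two layers.

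- **t-tests.** "For the efficacy test, we conducted t-test to compare outcome variables across T1 to T3, and changes between time points", the last of these in full being "changes between time points (T2-T1, T3-T2, T3-T1) between the two groups".
- **DID.** "We also conducted difference in difference (DID) analysis using the *mixed* command in Stata", where "we first entered group, time and the interaction term of group and time", followed by covariates one at a time.

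The first t-test clause can be read in two ways. On reading A, levels at T1, T2 and T3 and the three changes are all compared between groups. On reading B, only the three changes are, and the level comparison runs over time. The section ranks no test above another and states no alpha, decision rule or multiplicity handling. None of the t-tests is described as adjusted for the T1 value.

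**The concern.** Several of these tests ask nearly the same question. The T2 level test and the T2-T1 change test both estimate the effect at the end of the 3-month intervention. They treat T1 differently, the first ignoring it and the second subtracting it in full. With few caregivers the two can easily part company, and the supplied text does not say which one carries the result. Both also give up precision that regression on the T1 value would recover.

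Running them side by side gives more than one chance of a favourable result on each outcome. On reading A, the T1 significance test adds nothing, because randomisation already makes its null hypothesis true.

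At stake are the width of the pilot's intervals and whether a reader can tell which estimate to quote.

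**Working it through.** **Inputs from the documents.** The Sample section gives 19 versus 19 randomised. The Analysis section reports three caregivers without T2 and T3 data, one in the intervention group and two in the control group. Completers are therefore 19 − 1 = 18 and 19 − 2 = 17, or 35 in all. The documents give no error rate, power or precision figure to reproduce.

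**Assumptions.** Normal outcomes with SD 1 at each time, pooled t-tests, two-sided 5% per test, and correlation r = 0.3 to 0.8 for precision and power. For the error rates, r runs from 0 to 0.9 (equal correlation) or 0.3 to 0.9 (AR(1)).

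**Precision at T2.**

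- Level: t(0.975, 33 df) × √(1/18 + 1/17) = 2.0345 × 0.3382 = 0.688 SD with SD fixed at 1. Averaged over estimated SDs in simulation it is 0.68.
- Change: level × √(2(1 − r)). At r = 0.3, 0.68 × 1.183 is about 0.81. At r = 0.8, 0.68 × 0.632 = 0.43.
- T1-adjusted: level × √(1 − r²), plus a small cost for the lost degree of freedom and chance imbalance in T1. At r = 0.3, 0.68 × 0.954 = 0.65, and simulation gives 0.66, a cost of about 2%. At r = 0.8, 0.68 × 0.6 = 0.41, and simulation gives 0.42.

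| r | Level | Change | T1-adjusted |
|---|---|---|---|
| 0.3 | 0.68 | 0.81 | 0.66 |
| 0.8 | 0.68 | 0.43 | 0.42 |

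From the unrounded simulated values (level 0.683; change 0.809 and 0.432; adjusted 0.663 and 0.417), the adjusted interval is 3% to 39% narrower than the level interval and 3% to 18% narrower than the change interval. The gain over the level test is small at low r, and the gain over the change test is small at high r.

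**Power and disagreement, assumed 0.5 SD benefit at T2.** Power is 30% for the level test, 23% to 62% for the change test and 32% to 65% for the adjusted comparison. The level and change tests disagree on favourable significance in 25% of trials at r = 0.3 and 47% at r = 0.8.

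**False favourable chance per outcome, no true effect.** A trial counts if at least one test in the set is significant in the favourable direction. This success rule is assumed.

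| Tests counted | Chance |
|---|---|
| Levels at T2 and T3 plus all three changes (reading A) | 9.2% to 10.1% |
| Three changes only (reading B) | 6.0% to 6.7% |
| Reading A without T3-T2 | 7.6% to 8.3% |
| Reading B without T3-T2 | 4.2% to 4.7% |
| One pre-named contrast | 2.5% |

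For reference, independent tests would give 1 − 0.975⁵ = 11.9% for five and 1 − 0.975³ = 7.3% for three. The overlap lowers these only modestly. The T1 test, the DID model and the number of outcomes are not counted.

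**DID.** In completers with time as categories (assumed; the coding is not stated), the group-by-time interactions estimate the same differences as the T2-T1 and T3-T1 change tests, with different standard errors. DID therefore repeats those contrasts and does not supply the T1-adjusted one.

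**The case against.** **It is a finished pilot.** The section is in the past tense, feasibility is listed first, and naming a lead contrast now restores no error control. This stands and limits the point. It does not affect the precision gain, which is available from data already held, and the section does call this part an efficacy test.

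**The error rates need a rule that the documents lack.** This also stands. A reader might infer that the trial had a 9% to 10% false favourable risk. The documents do not support that as a fact, because no alpha and no any-one-test rule is stated. The lower figures of about 8% and 4% to 5% require leaving out T3-T2, which the plan lists. Leaving it out is arguable, since that change starts when the 3-month mentoring ends, but it is a choice to be declared.

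**A lead outcome or contrast may be named elsewhere.** A reader might infer that none exists. The supplied text has no aims, measures or results section, so the absence can be claimed only for what is supplied.

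**DID may be the intended lead.** The remark that covariates left the main findings unchanged follows the mixed-model description. This is suggestive, but it is not a designation. DID rates are left out above because a random-intercept model with large-sample tests can mix misfit with multiplicity.

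**Burden is not obviously the lead outcome.** A reader might choose it because eligibility required "having moderate to severe caregiver burden" and the missing-data account names it among the measures ("most measures (e.g., caregiving burden, caregiving competency) were not applicable to them"). The Procedure and Intervention sections, however, give the aim as reducing caregivers' stress. Selecting on burden also narrows its T1 range and tends to lower r, towards the end where adjustment gains only 3% over the level test.

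**The larger trial.** The Procedure section reports presenting results to the community "for their comments to improve the intervention for a larger-scale test". It does not say that such a test would take its contrast from this analysis.

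**Conclusion.** The point holds, and it rests chiefly on precision. For r between 0.3 and 0.8, a T1-adjusted comparison at T2 is at least as precise as either t-test, and it replaces two tests that would disagree in a quarter to nearly half of trials under an assumed 0.5 SD benefit. If r were below about 0.2, the roughly 2% small-sample cost would cancel the gain over the level test, since √(1 − 0.2²) = 0.98.

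The multiplicity part is conditional. Under an assumed any-one-test rule at two-sided 5%, the chance per outcome is about 9% to 10% on reading A or 6% to 7% on reading B, against 2.5% for one pre-named contrast. The assumed correlation changes these little. The risk across outcomes would be higher but cannot be sized without the outcome list.

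**What to change.** - State whether the T1 to T3 comparison is between groups or over time.
- Replace the level and change t-tests with one between-group comparison at T2 adjusted for the T1 value, with the same comparison at T3 as secondary.
- Apply it to the primary outcome if one is named elsewhere. If none is, use the measure that best matches the stated aim of reducing caregiver stress.
- Drop the T1 significance test.
- Report T3-T2, DID and all other outcomes as exploratory estimates with 95% CIs.
- Label the lead contrast post hoc unless an earlier plan named it, and say that the label does not restore type I error control here. Pre-specify the contrast in any larger-scale test, where the 2.5% would apply.

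**Cost.** One regression per time point on data already held. Fewer contrasts can be called significant, and the adjustment assumes a common T1 slope in both groups with only 35 completers.

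### No stated efficacy analysis adjusts for the T1 outcome with an estimated slope, so precision is lost if the true slope lies between 0 and 1; the size depends on a correlation the document does not give

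*Combined protocol and SAP*

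**What the plan says.** The Analysis section of the combined protocol and SAP describes three kinds of efficacy analysis.

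- **t-tests:** "we conducted t-test to compare outcome variables across T1 to T3, and changes between time points (T2-T1, T3-T2, T3-T1) between the two groups".
- **Mixed model:** "We also conducted difference in difference (DID) analysis using the *mixed* command in Stata". For its fixed part, "we first entered group, time and the interaction term of group and time".
- **Covariates:** the authors "then entered covariates, such as sociodemographic, health, acculturation and caregiving variables, one by one due to the small sample size". The section reports that none altered the main findings and does not give those parameters.

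The covariate types named do not include the T1 value of the outcome, and no ANCOVA or common-baseline model is described. The time coding, covariance structure and estimator of the mixed model are not stated, nor is any SD, correlation, effect size or power.

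The Sample section gives 19 caregivers per group. The Analysis section reports three without T2 and T3 data: "Two caregivers (one in the intervention group and the other in the control group) lost their care recipients during the intervention time", and one further control caregiver withdrew. That leaves 18 intervention and 17 control caregivers at follow-up.

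**The concern.** A follow-up comparison can use the T1 outcome in three ways: ignore it (slope 0), subtract it in full (slope 1), or let the data choose the slope. The plan uses the first two and not the third. With 35 caregivers followed, a sizeable chance difference at T1 is likely. If the true slope is between 0 and 1, ignoring T1 under-corrects for that difference and subtracting it over-corrects. Follow-up and change results then move apart for a reason unrelated to mentoring, and the section names no main analysis to settle which to read. The t-test at T1 can reveal an imbalance but does not correct for it. The T1 data needed for the correction have already been collected.

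**Working it through.** The document states no figure to reproduce, so the check has two parts: what slope each analysis imposes, and what that costs over a range of assumed r.

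**1. Slope imposed by each analysis**

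| Analysis | Slope on T1 |
|---|---|
| t-test at T2 or T3 | 0 |
| t-test on T2-T1 or T3-T1 | 1 |
| t-test on T3-T2 | no T1 term |
| DID, group by time | 1 |

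The DID entry was checked by generalised least squares with a random intercept, 19 vs 19 at T1 and 18 vs 17 at T2 and T3. The weight on T1 is -1.00 with three-level time, -1.00 with T2 and T3 pooled, and -0.50 per visit (-1.00 from T1 to T3) with linear time. With complete data and three-level time, the T2 interaction equals the T2-T1 difference exactly. Keeping the three T1-only caregivers lowers its variance only slightly, for example from 1.00 to 0.98 at r = 0.5 in the units below.

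**2. Variance of the group difference**

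Units are SD² × (1/18 + 1/17), with equal SDs at T1 and follow-up assumed.

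- Follow-up score: 1
- Change score: 2(1 - r)
- ANCOVA: (1 - r²) × (1 + 1/31), the second factor (1.032) being the average cost of estimating the slope with 35 caregivers

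| r (assumed) | Follow-up | Change | ANCOVA | ANCOVA / better of the two |
|---|---|---|---|---|
| 0.1 | 1.00 | 1.80 | 1.02 | 1.02 |
| 0.3 | 1.00 | 1.40 | 0.94 | 0.94 |
| 0.5 | 1.00 | 1.00 | 0.77 | 0.77 |
| 0.6 | 1.00 | 0.80 | 0.66 | 0.83 |
| 0.7 | 1.00 | 0.60 | 0.53 | 0.88 |
| 0.9 | 1.00 | 0.20 | 0.20 | 0.98 |

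Break-even is r = 0.18 against follow-up scores (1.032(1 - r²) = 1) and r = 0.94 against change scores (1.032(1 + r)/2 = 1).

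**3. Chance imbalance at T1**

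SE of the T1 difference = √(1/18 + 1/17) = 0.338 SD. The chance of exceeding 0.3 SD in either direction is P(|Z| > 0.3/0.338 = 0.887), about 37%.

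With an imbalance of 1 SE and r = 0.6, the follow-up estimate shifts by 0.6 × 0.338 = +0.20 SD and the change estimate by -0.4 × 0.338 = -0.135 SD. The adjusted estimate does not shift.

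**4. Cost of adjustment given the imbalance**

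For an imbalance of z standard errors, the mean variance inflation of ANCOVA is about z²/31. Averaged over all trials (mean z² = 1) it is 3%. Among trials with imbalance above 0.3 SD (mean z² = 2.27) it is 7%; at z = 2 it is 13%.

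Mean squared error in those imbalanced trials, same units as step 2:

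- Follow-up: 1 - r² + 2.27r²
- Change: 1 - r² + 2.27(1 - r)²
- ANCOVA: (1 - r²)(1 + 2.27/31)

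| r | Follow-up | Change | ANCOVA |
|---|---|---|---|
| 0.5 | 1.32 | 1.32 | 0.80 |
| 0.6 | 1.46 | 1.00 | 0.69 |
| 0.7 | 1.62 | 0.71 | 0.55 |

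**5. Burden entry rule**

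Entry required "having moderate to severe caregiver burden" (Sample section). Suppose this cuts the lowest 30% or 50% of T1 burden, with unrestricted r = 0.6. The T1 variance falls to k = 0.493 or 0.363 of its unrestricted value. ANCOVA relative to change is then 1.032 × 0.64/(0.64 + 0.16k) = 0.92 or 0.95. Relative to follow-up it is 1.032 × 0.64/(0.64 + 0.36k) = 0.81 or 0.86.

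**The case against.** The strongest reply is that this is a choice between valid methods. The document contains no contradiction or wrong number here, every size above rests on an assumed r and SD ratio, and this is a pilot whose Analysis section puts feasibility first. Much of that stands. The gain over the better existing test peaks at r = 0.5 and is small or slightly negative at either end of the range. With T1 SD at 0.6 to 0.8 of the follow-up SD and r = 0.7, the slope is 0.88 to 1.17 and the variance ratio against change scores is 1.01 to 1.03, so nothing is gained. What does not stand is that the choice is neutral: the plan reports both fixed slopes, and adjustment costs little on average.

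A second reply is that the mixed model already handles T1, or that its caregiving covariates might include the T1 outcome. The model estimates within-caregiver covariance, but its free group term leaves the T1 difference unconstrained. Adding the T1 score as a main effect, while T1 is also a response, would not turn the interaction into ANCOVA.

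Three stronger inferences are tempting and not supported:

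- *That the stated analyses are biased or invalid.* Under randomisation they are not, with two conditions. The first is ignorable missingness; two of the three losses followed a care recipient's death. The second is setting aside mentor clustering: "Each mentor was paired with one to three caregivers based on their language preference and similar caregiving experiences" (Intervention section). With 18 mentees shared by 8 mentors and an assumed mentor share of 0.05 to 0.2 of residual variance, simulated type I error is 5.3-6.6% for follow-up, change and ANCOVA alike, so clustering does not favour one over another.
- *That every change comparison is affected.* T3-T2 contains no T1 value.
- *That disagreement between follow-up and change tests is all due to T1.* In simulation at an assumed 0.8 SD effect and r = 0.5, 0.6 and 0.7, one is significant and the other not in 32-33% of trials. With imbalance below 0.05 SD the rates are still 11%, 13% and 19%.

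**Conclusion.** The point holds as one of precision and clarity, not validity. No stated efficacy analysis estimates the T1 slope. If the true slope lies between 0 and 1, the T2 and T3 t-tests, the T2-T1 and T3-T1 t-tests and the DID can each be less precise than a T1-adjusted estimate. With equal SDs and 18 vs 17 caregivers, the adjusted variance ranges from 23% lower than the better existing t-test (r = 0.5) to 2% higher (r = 0.1). For burden, truncation at entry would shrink the gain to about 5-8% against change scores under the assumptions shown.

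A reader might infer that this trial lost a known amount of precision. The document does not support that: r and the SD ratio are not given, so the loss here could be large or close to nil. The conclusion also rests on normal data, ignorable missingness and no allowance for mentor clustering. The change is worth making because the T1 data are in hand, the sample is small, and the Procedure and setting section looks ahead to a larger-scale test.

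**What to change.** - **Add an adjusted analysis, labelled post hoc.** Fit ANCOVA of T2 and of T3 on group plus the T1 value. Alternatively, fit the mixed model with three-level time, a common T1 mean (no group term at T1), unstructured covariance, REML and small-sample degrees of freedom. With the same caregivers seen at T2 and T3, both give the same point estimates.
- **Report it with a 95% CI beside the t-tests and DID already done.** It should not replace them, because choosing a new main estimate after results are known would be a further analyst choice.
- **Report the observed T1-to-T2 and T1-to-T3 slopes and correlations,** so readers can see how much adjustment matters and the next trial can be planned from them.
- **Prespecify the adjusted analysis as the main efficacy analysis of the larger-scale test.**

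The cost is one degree of freedom and the variance increase from estimating the slope: about 3% on average, about 7% on average when imbalance exceeds 0.3 SD, and about 13% near 2 SE. It is a reanalysis of existing data; nothing new need be collected.

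### Does leaving three of 38 randomised caregivers out of the follow-up t-tests, without imputation, undermine the efficacy comparison?

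*Combined protocol and SAP*

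**What the plan says.** The Sample section gives 38 caregivers, randomised 19 to each arm, with assessments at baseline (T1), 3 months (T2) and 6 months (T3).

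The Analysis section describes two efficacy analyses. The first is a set of t-tests: "For the efficacy test, we conducted t-test to compare outcome variables across T1 to T3", plus between-group tests on the three change scores. The second is a difference-in-difference analysis with Stata's mixed command: "In multilevel (observations nested in caregivers) linear regression models, we first entered group, time and the interaction term of group and time".

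On missing data it states: "We missed three caregivers' data at T2 and T3". One caregiver in each arm lost the care recipient, and for these two "most measures (e.g., caregiving burden, caregiving competency) were not applicable to them". The third, a control, left for lack of time. The section closes: "Given the purpose and sample size of this pilot study, we did not perform imputations or replications for missing data".

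The supplied text gives no number analysed for the multilevel model and no list of measures that would still apply after bereavement.

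**The concern.** The follow-up t-tests compare people selected after randomisation, and no sensitivity analysis shows how much that matters. With about 18 per arm, three people can decide a borderline result. The text calls this the efficacy test, and Procedure and setting says the pilot's results were taken back to the community "to improve the intervention for a larger-scale test", so the handling might be carried forward.

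Two further points sharpen the worry. First, the bereaved caregivers and the drop-out are treated alike, although an outcome that no longer exists is not the same as one that was not collected. Only most measures ceased to apply after the death, yet the follow-up data of all three are reported as missed. Second, the multilevel model could have used all 38 caregivers or only the 35 with follow-up, and the reader is not told which.

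**Working it through.** **Inputs from the documents.** 19 + 19 = 38 randomised (Sample). Losses at T2 and T3: 1 intervention (bereaved) and 2 control (1 bereaved, 1 drop-out) (Analysis). The documents give no SD, alpha, power or outcome values. A two-sided 0.05 level, a common SD and the size of any departure are therefore assumptions.

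**Counts.** 1 + 1 + 1 = 3 missing, as the plan states. 3/38 = 7.9%; by arm 1/19 = 5.3% and 2/19 = 10.5% (Fisher p = 1.0). At follow-up 19 − 1 = 18 against 19 − 2 = 17, or 35 in all. The multilevel model has 38 + 35 + 35 = 108 records if all available data enter, and 3 × 35 = 105 if only completers do. The two versions differ by three baseline rows.

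**Precision.** SE of a mean difference in SD units = √(1/n₁ + 1/n₂).
- 19 vs 19: √(2/19) = 0.324
- 18 vs 17: √(1/18 + 1/17) = 0.338
- Ratio 0.338/0.324 = 1.042, an increase of 4.2%

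**Possible bias.** Suppose the missing caregivers differ from those observed in their arm by an assumed 1 SD, with the SE held at 0.338 SD.

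| Case | Shift (SD) | Shift / 0.338 (SE) |
|---|---|---|
| Burden, competency: the control drop-out only, bereaved excluded | 1/18 = 0.056 | 0.16 |
| All three, same direction | 2/19 − 1/19 = 0.053 | 0.16 |
| All three, opposite directions by arm | 1/19 + 2/19 = 0.158 | 0.47 |

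**Effect on a p-value.** The critical value of t on 18 + 17 − 2 = 33 degrees of freedom is 2.035.
- Drop-out only: an observed p = 0.05 becomes t = 2.035 − 0.164 = 1.870, p = 0.070. To stay significant, a result needs t of at least 2.035 + 0.164 = 2.199, which is p = 0.035 or smaller.
- All three opposed against the effect: t = 2.035 − 0.467 = 1.568, p = 0.127. To stay significant, a result needs t of at least 2.501, which is p of about 0.018 or smaller.
- The same opposed shift in favour of the effect takes p = 0.05 to about 0.018.

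For an observed p = 0.03 to reach 0.05, the difference must move by 0.079 SD. That takes 0.079 × 18 = 1.42 SD from the drop-out alone, or 0.079/(3/19) = 0.50 SD from each of three caregivers, all against the effect.

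**Which case applies.** The only measures the section names as examples are burden and competency. These are undefined once the care recipient has died, so the first row of the table is the relevant one. The third row needs a measure that still applied after bereavement, and the supplied text names none.

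**The case for a change.** The strongest case for a change is that bereavement and drop-out call for different handling, and that saying so needs no extra participants. Death of the care recipient is foreseeable in dementia caregiving and occurred in 2 of 38 here. If any general measure still applied, leaving the bereaved out breaks the randomised comparison without need. A small pilot does not excuse an unstated analysis set, and one extra table would show how robust the results are.

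Part of this stands. The number in each model should appear, and a sentence on whom the caregiving-specific effects describe would help the reader and the larger test. The rest does not lead to a different analysis:

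- Reanalysing the bereaved needs both a measure that still applied and data on it. The text says their follow-up data were missed, so there may be nothing to restore.
- Ranking the multilevel model above the t-tests gains almost nothing. It is already run, a likelihood fit is valid without imputation if data are missing at random, and a caregiver seen only at baseline says little about change.
- The p = 0.127 figure stacks three assumptions: a full SD for each person, arms opposed, and all against the effect.
- The 1 against 2 split is a difference of one person, and bereavement itself is balanced at one per arm.
- The supplied text covers methods and refers to itself as a paper. Numbers analysed and lists of measures usually sit in results tables and a measures section, which are not among the supplied pages. Their absence here is weak evidence of a gap.

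**Conclusion.** No change to the plan is needed. The authors disclose how many caregivers were lost, when, in which arm and why. They decline to impute, which is right for burden and competency after the care recipient's death, and they already run a model that can use every available record.

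For those measures the exposure is one control drop-out: 0.056 SD or 0.16 SE at an assumed 1 SD departure, enough to matter only for observed p-values of about 0.035 to 0.05. The documents report no such result. A shift analysis is optional.

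The conclusion rests on two assumptions: that the multilevel model was fitted to all available records, as its usual use implies, and that no measure with usable follow-up data from the bereaved was set aside. Stating n by arm and time point for each analysis, and saying that caregiving-specific effects apply while care continues, would settle both as matters of reporting. Neither omission makes the results unsound.
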